3. DATA COLLECTION

3.1 KEY OUTCOMES

This section describes the key outcomes and unit of analysis. Each research question focuses on different indicators based on the data collected. The pre-analysis plan in Appendix 1 describes the analytic model and metrics for each research question in more detail. Some indicators for the process evaluations will be based on data collected during nudge installation. The remaining indicators will be based on observed data collected during the end-line.

The primary research question (RQ1) will specifically target two groups of pupils at sample schools: pupils from grade 1-3, and pupils from grade 4-6. UNICEF and DepEd are interested in the potentially different impact of the intervention on pupil iHWWS in both of these grade groups, in order to inform in which grades to implement the nudges in the future. The impact may differ between these two groups due to different receptiveness to motivators for handwashing behavior targeted by the nudges, or different pre-existing pupil behaviors and perceptions around handwashing. The two age groups were identified in collaboration with UNICEF and are in line with the distinction often made in schools between "lower grades" (1-3) and "higher grades" (4-6). We will report estimates for the pooled sample, but will also conduct sub-group analysis to determine whether the impact of the key outcomes for this research question was statistically significantly different in the two samples.

In addition, within each sample, sub-group analysis will be conducted to compare the average impact of the behavioral nudges by:

- pupil gender
- enumerator gender
- WinS implementation quality index score
- whether the handwashing environment is conducive to nudges, as determined by a constructed index on homogeneity of the toilet and handwashing environment (see Table)
- class size

More information on the analytic models used for each research question, sub-group analysis and covariates included is provided in the pre-analysis plan in Section 6. An overview of the key indicators, unit and sample for each research question is presented in Table 1 below.

Table 1: Key Outcomes by Research Question

RQ.	Outcome category	Outcome	Unit (sample)
RQ1 Independent (impact) handwashing after toilet use		Pupil washed hands with soap and water after toilet use	Pupil (grade 1-3 & grade 4-6)
		Pupil washed hands with water after toilet use	Pupil (grade 1-3 & grade 4-6)

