1. iHWWS rates (impact evaluation, RQ1)	iHHWS after toilet use observations in classroom (treatment & control)	4 months post- implementation	Enumerators will observe whether pupils wash their hands with soap, wash without soap, or do not wash, after they have used classroom toilets. This will be used to estimate the causal impact of the nudges intervention on iHHWS rates.
2. Homogeneity in toilet and handwashing environment (impact evaluation, RQ1)	Structured facilities observations for both treatment and control (treatment & control)	4 months post- implementation	Structured observations of each facility will assess factors such as: presence of existing WASH-related informational posters, whether the handwashing area is used for other non-WASH purposes (e.g. storage, dish-washing area), whether the handwashing station has objects unrelated to handwashing ³³ , how many primary colors are present in health corner where handwashing station is present, and other factors related to visual clutter to be finetuned after piloting. These will be used to construct a measure of whether the facility is conducive to nudges, to be used in subgroup analyses.
2. Access to soap and water (impact evaluation, RQ2)	Structured facilities observations (Treatment & control)	4 months post- implementation	Structured observations of whether classroom handwashing facilities including soap and water. These will be used to estimate the causal impact of the nudges intervention on pupil access to soap.
3. Nudges implementation (process evaluation, RQ3)	Structured facilities observations (treatment)	During implementation visit but after nudge installations are completed	Structured observations of facility after implementation, to assess presence and condition of nudges in toilet and/or handwashing station. These will be used to assess if installation proceeded as intended.
4. Nudges implementation (process evaluation, RQ3)	Structured facilities observations (treatment)	4 months post- implementation	Structured observations of presence and condition of nudges in toilets and/or handwashing facilities. These will be used to assess if installed nudges functioned and lasted as expected.

³³ A concern is that handwashing areas both across and within schools may differ in terms of how conducive they are to nudges; more cluttered and busy environments may dilute the impact of nudges.

Pre-analysis plan [DRAFT] | January 20, 2020

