4. TECHNICAL RISKS AND MITIGATION STRATEGIES

"Clutteredness" in school handwashing environment

Schools in our sample may differ in terms of baseline toilet and handwashing facility environments. A potential concern is that among handwashing areas that are cluttered and busy, all nudges by the handwashing area (footpath, arrow sticker, eye sticker) would be less likely to grab attention by producing the necessary element of surprise; therefore, any potential impact of the intervention may be diluted. This is particularly likely if the bathrooms already have existing WASH-related informational posters, are crowded with other features (e.g. cabinets or items for storage), or used for other purposes such as tooth-brushing or cleaning dishes. Since we hypothesize that baseline bathroom "clutteredness" factors like these mediate the impact of nudges, substantial differences in the toilet/handwashing environment present the risk of reducing the impact of nudges overall. If the average school is very cluttered, we may not have a large enough sample size to estimate the differential effects of the nudges in cluttered schools and uncluttered schools.

We address this risk in two ways:

1) During school sampling, we prioritized selecting schools with "nudge enabling" handwashing environments, based on characteristics available in the OMS data which we hypothesized could reflect conduciveness to nudges. This is described in Section 2.5 Recruitment of Participants (Sampling).

2) Given that OMS data is at the school-level and there may be difference within a school in terms of handwashing facilities, during our endline data collection, we will also collect detailed information on toilet and handwashing facility environment. Using this data, we will explicitly model for heterogeneity of "nudge enabling" environments in our analysis of the impact of nudges.

Observer effects and social desirability bias

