Class	Number of pupils in the classroom	X.5 – continuous variable where value represents the number of pupils present in the classroom during the observation period	Classroom size may be associated with school resources and teacher quality or attention, which may influence pupil opportunity and incentives to wash hands with soap. Further, if handwashing with soap after toilet use is considered to be a norm (or habit) that the nudges remind pupils of, and if the class is considered as the primary 'social unit' for this norm, the number of pupils in this social unit may influence the likelihood of the norm arising and persisting.

Table 4: Control Variables for Research Question 1

³⁷ This variable may be converted to an ordinal variable to mitigate random error due to imprecision in the number of pupils reported.

³⁸ See Table 7 in the *Sampling* section of the evaluation design document for a description of 11 indicators an additional information on the online monitoring system (OMS) Evaluation Design Document

Pre-analysis plan [DRAFT] | January 20, 2020

	Nudge- conducive	X.6 - Binary variable indicating whether the handwashing area location near/in the classroom is "nudge conducive"	Nudge-conducive handwashing areas are those with combinations of features that indicate they may be more conducive to nudge intervention than handwashing areas without those features. Please see Section 3.2 Data Collection Activities for details of these nudge-conducive features. The nudge intervention may have greater impact for nudge-conducive handwashing areas than non-nudge conducive areas.
Unit	Co-variate	Metric	Hypothesized relationship to outcome
Pupil	Gender	X.7 – binary variable for whether pupil observed is female	Traditional gender roles tend to involve more tasks that may require handwashing for girls than boys, such as cooking or cleaning, and may thus facilitate building handwashing habits among girls.
	Grade	X.8 – categorical variable where each	The behavioral nudges targeted at changing pupil behavior may be more engaging and/or effectively

1.c. Analytic model

Specification for LPM: The effect of the treatment on the outcome variables listed in **Error! R** eference source not found. for which the analytic model indicated is the Linear Probability Model will be measured by conducting the following regression:

$$Y_{ij} = \beta_0 + \beta_1 T_j + \overrightarrow{\beta_2} \vec{X}_{2ij} + \varepsilon_{ij}$$

Where:

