 $^{^{\}rm 39}$ Observations in which the student grade was unknown will be excluded.

Pre-analysis plan [DRAFT] | January 20, 2020

1.d.iv. Treatment impact by WinS implementation quality index score: In order to compare the average effect of the nudges intervention on the outcome of independent handwashing after toilet use across different levels of WinS implementation quality, sub-group analysis will be conducted using the following regression:

$$Y_{ij} = \beta_0 + \beta_1 T_j + \beta_2 W_j + \beta_3 (T_j \times W_j) + \overrightarrow{\beta_4} \overrightarrow{X}_{4ij} + \varepsilon_{ij}$$

Where:

- *W_j* is an ordinal variable between 0 and 11 denoting the WinS implementation quality index score for school *j*
- \vec{X}_{4ij} represents a vector of pupil, school, and class level co-variates as specified in Table 2, excluding WinS implementation quality index score
- All other regression terms are defined as they were in the previous regression specification and β₃ is the coefficient of interest.

1.d.v. Treatment impact by nudge conduciveness: In order to compare the average effect of the nudges intervention on the outcome of independent handwashing after toilet use depending on the context's conduciveness to nudges, sub-group analysis will be conducted using the following regression:

Where:

$$Y_{ij} = \beta_0 + \beta_1 T_j + \beta_2 W_j + \beta_3 (T_j \times N_i) + \beta_4 X_{4ij} + \varepsilon_{ij}$$

- N_i will be a binary variable (to be constructed after seeing the distribution) =1 if the pupil
 was exposed to a nudge-conducive handwashing environment at the time of toiet use and
 =0 if not
- \vec{X}_{4ij} represents a vector of pupil, school, and class level co-variates as specified in Table 2, excluding WinS implementation quality index score
- All other regression terms are defined as they were in the previous regression specification and β₃ is the coefficient of interest.

1.e. Presentation of results: a regression table will be included for each specification to describe the correlation between key indicators of interest and co-variates. Data visualizations describing the level of the outcomes variables in the treatment and control group may also be included.

RESEARCH QUESTION 2

2.a Research question 2: What is the causal impact of the behavioral nudge intervention on pupil access to handwashing facilities with soap and water?

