- L_k is a dummy variable denoting whether toilet facility k is located inside a classroom
- \vec{X}_{4j} represents a vector of school level co-variates as specified in sub-section 2.b, excluding location of toilet facility
- ϵ_{kj} denotes the facility error term k, clustered at the school-level to reflect the fact that the treatment assignment was at the school level
- β_n denotes the coefficients determined by the regression model (β₃ is coefficient of interest)

2.d.ii. *Treatment impact by WinS implementation quality index score*: In order to compare the average effect of the nudges intervention on the outcome of presence of a functioning handwashing facility with soap near school toilets across different levels of WinS implementation quality, sub-group analysis will be conducted using the following regression:

$$Y_{kj} = \beta_0 + \beta_1 T_j + \beta_2 W_j + \beta_3 (T_j \times W_j) + \overrightarrow{\beta_4} \vec{X}_{4kj} + \varepsilon_j$$

Where:

- W_j is an ordinal variable between 0 and 11 denoting the WinS implementation quality index score
- \vec{X}_{4kj} represents a vector of school and facility level co-variates as specified in sub-section 2.b, excluding WinS implementation quality index score
- All other regression terms are defined as they were in the previous regression specification and β₃ is the coefficient of interest

2.e. Presentation of results: a regression table will be included for each specification to describe the correlation between key indicators of interest and co-variates. Data visualizations describing the level of the outcomes variables in the treatment and control group may also be included.

MULTIPLE HYPOTHESIS TESTING CORRECTION

Subgroup analyses and analyzing multiple indicators of the same category of outcomes increases the number of hypotheses being tested. As such, standard statistical significance levels would likely result in finding significant coefficients by chance alone (i.e., false positives). To correct for this increased likelihood of false positives, the analysis will be adjusted for multiple inference using the

Holm-Bonferroni procedure⁴¹. The correction will impose a more conservative threshold for statistical significance. Normal, uncorrected p-values will also be reported.

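### The conduciveness index in 1.d.v is cut to a yes/no flag after endline data are seen, with no rule and no requirement to set the cut before outcomes or arm are linked

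*SAP*

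**What the plan says.** SAP section 3.1 lists conduciveness of the handwashing environment as a subgroup factor, "as determined by a constructed index on homogeneity of the toilet and handwashing environment". Table 2 in section 3.2 names the ingredients: existing WASH posters, use of the area for other purposes, unrelated objects, the number of primary colours, and "other factors related to visual clutter to be finetuned after piloting". Of these observations it says: "These will be used to construct a measure of whether the facility is conducive to nudges, to be used in subgroup analyses". Table 2 times them at 4 months post-implementation, the same time as the handwashing observations. Section 4 confirms this: "during our endline data collection, we will also collect detailed information on toilet and handwashing facility environment".

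In section 6, 1.d.v, the index becomes a 0/1 moderator N_i that "will be a binary variable (to be constructed after seeing the distribution". No cut-off, no rule such as a median split, no separation from outcome or arm, and no analysis of the uncut index is given there or elsewhere. A binary conduciveness variable also appears as covariate X.6 in Table 4, again without a cut-off.

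The subsection just before, 1.d.iv, treats the plan's other index differently: W_j "is an ordinal variable between 0 and 11 denoting the WinS implementation quality index score" and enters its interaction uncut.

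Table 6 counts nudge conduciveness as one of four RQ1 subgroup hypotheses for the Holm–Bonferroni correction.

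**The concern.** The Introduction says the plan was written before endline outcome collection, so its purpose is to settle such choices in advance. Here the choice is deferred to a time when outcomes and arms will be in the same hands as the index. Even if the cut is set honestly, a reader of the results could not verify that from the plan.

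The analysis is not incidental. Section 2.6 explains that schools likely to be uncluttered were oversampled and that the interest lies in clutter at facility level. Section 4 promises to model this heterogeneity and warns that the sample may be too small to do so if most schools are cluttered. A very uneven split would add to that difficulty. The Holm correction counts the moderator once, however many cuts are looked at.

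**Working it through.** **The plan's own figure.** The SAP gives no power figure for this interaction. Its main-effect inputs (section 2.5) are 10% against 17%, ICC 0.1, 26 pupils per school, alpha 0.05 (two-sided assumed) and power 0.80. They reproduce:

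- Design effect: 1 + (26 − 1) × 0.1 = 3.5.
- Pupils per arm, unpooled variance: (0.10 × 0.90 + 0.17 × 0.83) × (1.960 + 0.842)² / 0.07² = 370.
- Schools per arm: 370 × 3.5 / 26 = 49.8, so 100 in total, as stated. The pooled formula gives 373 pupils and 50.2 schools per arm.

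These inputs are carried into the checks below with the final 132 schools.

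**Assumptions.** The SAP gives no distribution for the index. I took a classroom-level index over six classes per school, either normal or a 0–8 count, with 20–50% of its variance between schools. The model is the linear probability interaction model with school-clustered errors and no covariates.

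**1. Type I error with no true interaction** (nominal 5%, uncorrected p-value, 2,000 runs each):

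| How the moderator is formed | Normal index | 0–8 count index |
|---|---|---|
| Uncut | 4.9–5.0% | 5.4% |
| Fixed median cut | 4.7–5.2% | 4.8% |
| Most significant of 3 cuts (quartiles) | 11.9–12.6% | 12.8% |
| Most significant of 9 cuts (deciles) | 24.2–26.7% | 16.5% |

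A second simulation with 24 observations per school and 30% between-school index variance gave 6.2%, 5.8%, 12.9% and 24.8% down the normal-index column. With an assumed five-level index and the better of two central cuts, the rate was 7.9% (800 runs).

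**2. Information kept by a split, if modification is linear.** For a normal index cut at quantile q, the fraction kept is φ(z_q)² / [q(1 − q)]:

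- median: 0.399² / 0.25 = 0.64
- quartile: 0.318² / 0.1875 = 0.54
- 10/90 split: 0.1755² / 0.09 = 0.34

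**3. Power, linear truth, 132 schools** (1,000 runs each):

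- 3 pp per SD: 46% uncut, 36% median split.
- 4 pp per SD: 69% uncut, 55% median split. The second simulation gave 66% and 53%, and 44% for a cut at the 20th percentile.

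**4. Power, step truth.** With an assumed 8 pp difference in effect at the median, the flag had 71% power and the uncut score 49%. The same set-up with a linear truth of 4 pp per SD gave 53% for the flag and 70% for the score, in line with step 3. The reversal is expected. A normal score and its median split correlate at √(2/π) = 0.80, so each keeps 0.80² = 0.64 of the information when the other is the true form.

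**The case against.** The strongest objection is that the distribution in 1.d.v most naturally means the distribution of the index. Section 4 gives an innocent reason to look at it: to see whether enough facilities fall on each side. A cut set that way does not inflate the error rate, as the median-cut row shows. This stands. A reader might infer that the plan will test at 13% or 25%, but the SAP nowhere proposes to choose a cut by its result. Those rates only bound what the missing rule leaves possible, and several named items are presence/absence features, so a short index may offer few cuts.

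A reader might also infer that any cut costs power. That is not supported either. It depends on modification being roughly linear, the SAP states no shape, and its own language (conducive or not) is compatible with a threshold. The case for the uncut score is that it needs no cut and matches 1.d.iv, not that it always has more power.

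Finally, clutter should not be called the plan's principal modifier. Section 2.6 describes the handwashing environment as an important mediator, and the variable it singles out for balance is the WinS stratum.

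What survives is that the rule is absent, index and outcome are collected together, and no safeguard is written down.

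**Conclusion.** The point holds as a gap in pre-specification. The cut is deferred until after endline data are seen, and nothing ties it to the index alone. A cut blind to outcome leaves the test near 5%. A cut chosen on the result would give about 12–13% (best of three) or about 25% (best of nine) under an assumed normal index, and less for a short discrete index with few usable cuts. The efficiency argument is conditional: about 36% of the information is lost at the median if modification is linear, with the advantage reversed if there is a true step there.

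The scope is one secondary test in a Holm family of four. The pooled primary effect is not in question. X.6 is only a covariate in the adjusted model, and section 6 says estimates without controls will also be reported. The error and power figures rest on the assumed index distribution, which the SAP does not give.

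**What to change.** - In 1.d.v, enter the conduciveness index uncut, with its main effect and its interaction with T_j, and name that interaction as the Table 6 test. Write the main effect explicitly, since the printed equation shows W_j in that position.
- Keep any yes/no flag as a descriptive check and fix its rule now. One option is the observed index value that splits control-school facilities most evenly, which copes with ties in a short index. Compute it from the facility file before merging with handwashing outcomes.
- State that the installed nudges are excluded from index scoring. Signage and a coloured pathway are part of the intervention (section 1.2.1), and posters and colours are index items, so scoring them could shift treated facilities on the index.

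The cost is SAP wording only, with no new data. The downside is the linearity assumption of the uncut term. The descriptive split gives a check on it, and the step result above shows it should be reported alongside.

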Unit	Co-variate	Metric	Hypothesized relationship to outcome
	District Number of pupils enrolled (pre- intervention)	 X.1 – categorical variable where each value category represents the school district where the school is located X.2 – continuous variable to represent the number of pupils enrolled at the elementary school prior to intervention³⁷ X.3 – index variable between 0 and 11 	 School district is associated with geographic location, which may be associated with varying levels of rurality, access to water, socio-economic status of teachers and pupils, or support received from DepEd division office. Given that school budget is partially determined by number of pupils enrolled, and that larger schools tend to be located in urban or semi-urban areas, school resources and the school pupil and teacher population may vary depending on school size. This will be estimated using information reported by principals during end-line school visits or using the data reported in DepEd's Online Monitoring System (OMS), depending on how reliably information reported by principals can be collected.
School	WinS implementatio n quality index score (pre- intervention)	composed of 11 binary indicators related to WASH conditions at the school, as reported in OMS data by principals prior to the intervention ³⁸	Higher score indicates a higher level of reported quality of WinS implementation, and may thus be associated with a higher level of handwashing infrastructure and supplies, as well as more consistent implementation of WinS program activities involving pupils, such as group handwashing and tooth- brushing.
	Nudge- enabled	X.4–binary variable for whether school is "nudge-enabled" or not "nudge-enabled"	Nudge-enabled schools are those with combinations of features that indicate they may be more conducive to nudge intervention than schools without those features. Please see Section 2.5 Recruitment of Participants (Sampling) for details of these nudge-enabling features. Because of the presence of these features, the nudge intervention may have greater impact on nudge-enabled schools than schools that are not.

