2.b. Indicators, unit of analysis and sample: Table 5 below provides a summary of the indicators for this research question, and the unit of analysis and sample corresponding to each indicator. These indicators are based on enumerator observations of toilet and handwashing facilities at the schools visited.

Table 5: Outcome indicators for Research Question 2

Outcome category	Outcome	Metric	Unit	Sample	Analytic model ⁴⁰ (LPM – linear probability model; OLS – ordinary least squares)
(a)	Availability of functioning handwashing facilities with soap	Y.1 – continuous variable where value represents the number of functioning handwashing facilities with soap at the school	School	All T&C schools	OLS with Y=Y.1
Availability of handwashin g facilities	Presence of functional handwashing facility with soap near toilet facility	Y.1 – binary variable for whether there is a functioning handwashing facility with water and soap inside classroom for classroom toilet facilities and within 10 meters of functioning toilet facility for block toilet facilities	Toilet facility	All toilet facilities at T&C	LPM with Y=Y.1
with water and soap	Presence of functional handwashing facility near toilet facility	Y.1 – binary variable for whether there is a functioning handwashing facility with water inside classroom for classroom toilet facilities and within 10 meters of functioning toilet facility for block toilet facilities		school	LPM with Y=Y.1

⁴⁰ Unless otherwise stated, the independent variable of interest is treatment assignment.

The analytic model used to answer research question 2. will also include the following co-variates, as they were defined in the analytic model for research question 1 (see Table 4):

• School-level variables: school district; WinS implementation quality index score (preintervention)

In addition, for outcomes for which the unit indicated in Table 5 is the toilet facility and the analytic model is LPM, the following will be included as co-variates:

- School-level variable: number of pupils enrolled at the school (pre-intervention)
- **Facility-level variable:** Location of the toilet facility observed, defined as a categorical variable where each value category represents which of following location the classroom facility is inside a classroom from grade 1-6, or outside a classroom.

2.c. Analytic model

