2.c.i. *Specification for LPM:* The effect of treatment on the outcome variables listed in Table 5 for which the analytic model indicated is the Linear Probability Model will be measured by conducting the following regression:

$$Y_{kj} = \beta_0 + \beta_1 T_j + \overrightarrow{\beta_2} \vec{X}_{2kj} + \varepsilon_{kj}$$

Where:

- Y_{kj} denotes the outcome variable for facility k in school j, classified as a binary variable, as specified in Table
- *T_j* denotes the treatment variable (binary variable for whether school *j* received the nudges intervention)
- \vec{X}_{2ki} represents a vector of school and facility level co-variates as specified in sub-section 2.b
- ε_{kj} denotes the facility error term k, clustered at the school-level to reflect the fact that the treatment assignment was at the school level
- β_n denotes the coefficients determined by the regression model (β₁ is coefficient of interest)

2.c.ii. *Specification for OLS analytic model*: The effect of treatment on the outcome variables listed in Table for which the analytic model indicated is OLS will be measured by conducting the following regression:

$$Y_j = \beta_0 + \beta_1 T_j + \overrightarrow{\beta_2} \vec{X}_{2j} + \varepsilon_j$$

Where:

- *Y_j* denotes the outcome variable for school *j*, classified as a binary variable, as specified in Table
- *T_j* denotes the treatment variable (binary variable for whether school *j* received the nudges intervention)
- \vec{X}_{2i} represents a vector of school level co-variates as specified in sub-section 2.b
- ε_j denotes the school error term
- β_n denotes the coefficients determined by the regression model (β₁ is coefficient of interest)

2.d. Sub-group analysis

2.d.i. *Treatment impact by toilet facility location*: In order to compare the average effect of the intervention on the outcome of presence of a functioning handwashing facility with soap near school toilets between classroom toilets and out-of-classroom toilets, sub-group analysis will be conducted using the following regression:

$$Y_{kj} = \beta_0 + \beta_1 T_j + \beta_2 L_k + \beta_3 (T_j \times L_k) + \beta_4 \vec{X}_{4j} + \varepsilon_{kj}$$

Where:

- Y_{kj} denotes the outcome variable for toilet facility k in school j, classified as a binary variable, as specified in **Error! Reference source not found.**
- T_j denotes the treatment variable (binary variable for whether school *j* received the nudges intervention)

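### The RQ2 count of handwashing facilities with soap is modelled without enrolment, although the facility-level RQ2 models include it; the cost is precision, not validity

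*SAP*

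**What the plan says.** All points are in SAP section 6, Data Analysis, unless stated.

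- **Outcome.** Table 5 defines the school-level outcome as a "continuous variable where value represents the number of functioning handwashing facilities" with soap at the school. The unit is the school and the model is OLS. No per-pupil denominator or offset is given.
- **Covariates for every RQ2 model.** Section 2.b lists district and the pre-intervention WinS implementation quality score.
- **Extra covariates.** Enrolment and toilet location are added only "for outcomes for which the unit indicated in Table 5 is the toilet facility and the analytic model is LPM". That covers the binary presence outcomes and leaves out the count.
- **OLS specification.** In 2.c.ii the covariate term "represents a vector of school level co-variates as specified in sub-section 2.b", so nothing there brings enrolment back in. The same section says that the outcome term "denotes the outcome variable for school *j*, classified as a binary variable", which does not match Table 5.
- **Enrolment.** Table 4 defines X.2 as a "continuous variable to represent the number of pupils enrolled at the elementary school prior to intervention". Part of its stated rationale is that "school budget is partially determined by number of pupils enrolled". The source is either principals at end-line or the OMS, and a footnote allows conversion to an ordinal variable.
- **Randomisation.** Section 2.6 stratifies by three WinS bands, separately in nudge-enabled and other schools. Enrolment is not a stratification factor.

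**The concern.** Section 2.3 says that most DepEd schools have handwashing facilities in each classroom, and the note on sample weights for RQ1 recognises that schools differ in their number of classes. A school with more classrooms should therefore tend to have more facilities, and so more with soap, whatever its arm. Among the RQ2 outcomes in Table 5, the count is the one most directly tied to school size, yet it is the one modelled without a size term. The plan gives no reason. Its own argument for X.2, that resources follow enrolment, applies at least as well to a count of facilities as to a binary indicator at one toilet.

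At stake is the width of the confidence interval for one secondary outcome. Variation in size not captured by district or WinS score inflates the residual variance and makes a real change in the count harder to detect.

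**Working it through.** **1. The plan's own power figure.** The plan gives a calculation for RQ1 only, and it reproduces. Inputs from section 2.5: 10% against 17%, ICC 0.1, 26 pupils per school, alpha 0.05 (taken as two-sided), power 0.80.

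- Design effect: 1 + (26 − 1) × 0.1 = 3.5.
- Unpooled sample size per arm before clustering: (1.960 + 0.842)² × (0.10 × 0.90 + 0.17 × 0.83) / 0.07², which rounds up to 371.
- Schools per arm: 371 × 3.5 / 26 = 49.9. The pooled formula gives 373 pupils and 50.2 schools.

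Both agree with the stated 100 schools. Nothing comparable is stated for the RQ2 count: no SD, no enrolment distribution, and no correlation with enrolment.

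**2. Effect of adding enrolment.** With N schools in two equal arms and residual SD σ after district and WinS score, the standard error of the treatment coefficient is approximately σ × √(4/N). Adding X.2 multiplies it by √(1 − r²), where r is the partial correlation of the count with enrolment given district and WinS score. The equivalent increase in schools is 1/(1 − r²).

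The minimum detectable effect (MDE) at 80% power, in units of σ, is (1.960 + 0.842) × √(4/N) × √(1 − r²). Without enrolment this is 2.802 × √(4/132) = 0.49 for all 132 schools, and 2.802 × √(4/100) = 0.56 if the whole attrition buffer is lost.

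The values of r below are assumptions.

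| Assumed r | √(1 − r²) | Fall in SE | Equivalent schools | MDE, N = 132 | MDE, N = 100 |
|---|---|---|---|---|---|
| 0 (not adjusted) | 1.000 | 0% | 1.00× | 0.49 | 0.56 |
| 0.3 | 0.954 | 5% | 1.10× | 0.47 | 0.53 |
| 0.5 | 0.866 | 13% | 1.33× | 0.42 | 0.49 |
| 0.7 | 0.714 | 29% | 1.96× | 0.35 | 0.40 |
| 0.85 | 0.527 | 47% | 3.60× | 0.26 | 0.30 |

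Table 6 places this outcome in a Holm family of four. At Holm's strictest step, 0.05/4, the critical value is 2.498, and the unadjusted MDE with 132 schools is (2.498 + 0.842) × √(4/132) = 0.58.

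**3. Validity.** In 4,000 simulated trials of 132 schools with no treatment effect and counts driven by enrolment, the mean estimate was about 0 with and without adjustment. Type I error was 4.7% unadjusted and 5.0% adjusted. The inputs were invented (median enrolment 250, log-SD 0.6, about one facility per 30 pupils, half with soap) and there were no district or WinS terms. The simulation therefore supports the statement about validity but does not measure the gain in the planned model.

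**The case against.** The strongest reply is that this is a choice about efficiency. Schools are randomised, so leaving out a baseline covariate does not bias the intention-to-treat contrast, and chance imbalance in size is already reflected in the standard error. That stands. A reader might infer that the RQ2 result could be an artefact of school size, or that randomisation fails to balance size. The document supports neither: size was not a stratification factor, but randomisation still balances it in expectation.

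The size of the gain is also open. Table 4 links district to rurality and notes that larger schools tend to be urban or semi-urban, so district may already absorb part of the size effect. The outcome counts only working facilities with soap, so supply and upkeep matter as well as classroom numbers. Enrolment may be imprecisely reported. Each of these lowers r, and the gain could be as small as 5%. This point stands too.

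A reader might also infer that RQ2 could miss a change in soap access altogether. That goes too far. Table 5 also tests for a functioning facility with soap near each toilet; that model adjusts for enrolment and clusters by school, and both planned RQ2 subgroup analyses use that outcome.

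Finally, a per-pupil rate or a count model with an enrolment offset would be a reasonable alternative. This bears on the form of the remedy. It gives no reason to leave size out.

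**Conclusion.** The omission is clear from 2.b and 2.c.ii read together. It affects one outcome of a secondary research question, and it costs precision while leaving validity intact. The fall in standard error from adjusting runs from about 5% to 47% for assumed partial correlations of 0.3 to 0.85. The document does not show where in that range the trial lies, so the upper figures should not be read as expected gains. The case for the change is that it costs almost nothing, uses a variable the plan already defines and justifies by school size, and brings the count into line with the other RQ2 models. The binary label in 2.c.ii is a separate slip and adds no weight to this argument.

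**What to change.** In 2.b, state that X.2 (pre-intervention enrolment) is a covariate in the school-level OLS as well as in the facility-level LPMs, in the same form and from the same source as in the other models. Table 4 leaves the source and a possible ordinal conversion open, so settle both once for all models. If the count of functioning facilities without the soap condition, listed in Tables 1 and 6 but not in Table 5, is also modelled per school, give it the same covariate.

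Separately, in 2.c.ii, describe the outcome as the count defined in Table 5 instead of a binary variable.

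The cost is one sentence and one degree of freedom, or a few more if X.2 enters as ordinal categories. No new data are needed. The Introduction says that the plan's first version was written before endline outcome collection, so the covariate could be fixed without sight of the results.
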